9.5. Pharmacokinetics

Not applicable.

9.6. Pharmacodynamics

Not applicable.

9.7. Pharmacogenomics

Not applicable.

9.8. Biomarkers and Predictive or Other Analyses

9.8.1. Samples for Immunogenicity Testing

Blood samples for immunogenicity testing will be collected to determine antibody production against insulin lispro as specified in the Schedule of Activities (Section 2).

9.9. Health Economics

The self-reported questionnaires will be administered according to the Schedule of Activities (Section 2) in countries where the questionnaires have been translated into the native language of the region and linguistically validated.

9.9.1. EQ-5D-5L

The European Quality of Life – 5 Dimensions 5 Level (EQ-5D-5L; van Reenen and Janssen [WWW]) is a patient-rated questionnaire used to evaluate health status. The questionnaire consists of 2 parts. The first part assesses 5 dimensions (mobility, self-care, usual activities, pain/discomfort, and anxiety/depression) that have 5 possible levels of response (no problems, slight problems, moderate problems, severe problems, extreme problems). This part of the EQ-5D can be used to generate a health state index score, which is often used to compute quality-adjusted life years for utilization in health economic analyses. The health state index score is

calculated based on the responses to the 5 dimensions, providing a single value on a scale from less than 0 (where 0 is a health state equivalent to death; negative values are valued as worse than dead) to 1 (perfect health), with higher scores indicating better health utility. The second part of the questionnaire consists of a visual analog scale (VAS) on which the patient rates their perceived health state from 0 (worst imaginable health state/the worst health you can imagine) to 100 (best imaginable health state/the best health you can imagine).

9.9.2. Insulin Treatment Satisfaction Questionnaire

The Insulin Treatment Satisfaction Questionnaire (ITSQ; Anderson et al. 2004) is a validated instrument containing 22 items that assesses treatment satisfaction for persons with diabetes on insulin. Items are measured on a 7-point Likert-type scale, where lower scores reflect better outcomes. In addition to an overall score, the items that make up the 5 domains of satisfaction are categorized as:

- o Inconvenience of Regimen (5 items)
- o Lifestyle Flexibility (3 items)
- o Glycemic Control (3 items)
- o Hypoglycemic Control (5 items)
- o Insulin Delivery Device Satisfaction (6 items).

All individual patient-domain scores will be calculated as the mean of nonmissing items in the domain if <20% of the items within the relevant domain are missing; otherwise, the domain score will be missing. The domain scores will be transformed to a scale of 0 to 100 (derived as 100*[7-raw score]/6). An overall score is calculated as the mean of the nonmissing transformed domain score and only calculated when all 5 domain scores are nonmissing. A higher score indicates better treatment satisfaction.

9.9.3. Work Productivity and Activity Impairment Questionnaire General Health

The Work Productivity and Activity Impairment Questionnaire General Health (WPAI-GH; Reilly et al. 1993) consists of 6 questions to determine employment status, hours missed from work because of problems associated with diabetes, hours missed from work for other reasons, hours actually worked, the degree to which diabetes affected work productivity while at work, and the degree to which diabetes affected activities outside of work. Four scores are derived: percentage of absenteeism, percentage of presenteeism (reduced productivity while at work), an overall work impairment score that combines absenteeism and presenteeism, and percentage of impairment in activities performed outside of work. Greater scores indicate greater impairment and less productivity.

10. Statistical Considerations

10.1. Sample Size Determination

Approximately 350 patients will be randomized in order that 298 patients complete the study through the primary endpoint at Week 26.

The primary objective of this study is to test the hypothesis that LY900014 is noninferior to insulin lispro on glycemic control as measured by change from baseline to Week 26 in HbA1c in patients with T1D when administered in a double-blind manner as prandial insulin (0-2 minutes before meals) in combination with basal insulin.

Patients will be randomized in a 1:1 ratio to double-blind LY900014 dosed 0 to 2 minutes before meals, or double-blind insulin lispro dosed 0 to 2 minutes before meals. Assuming a non-inferiority margin (NIM) of 0.4%, no true difference between treatment arms, and an SD of 1.1%, 298 completers (149 in each treatment group) will provide 87% power to show noninferiority between LY900014 and insulin lispro in change from baseline to 26 weeks in HbA1c using the upper limit of a 2-sided 95% confidence interval (CI; LY900014 – insulin lispro). Assuming a 15% dropout rate for 26 weeks, approximately 350 patients will need to be randomized.

10.2. Populations for Analyses

For purposes of analysis, the following populations are defined:

Population	Description
Entered	All patients who sign informed consent.
Enrolled	All patients who receive at least 1 dose of open-label insulin lispro in the 8-week lead-in period.
Randomized	All patients who are randomly assigned to study treatment at Visit 8. Treatment group will be
	defined on the basis of the treatment the patients are assigned.
Safety	All randomized patients who receive at least 1 dose of the randomly assigned IP.
Completer	Patients included in the randomized population who have completed Week 26 of study treatment without permanent discontinuation of IP.
D D / 1	
Per Protocol	Patients included in the randomized population who have completed Week 26 of study treatment without permanent discontinuation of IP and without significant protocol deviations through
	Week 26 that would significantly impact the primary objective.
	Treatment group will be defined on the basis of the treatment the patients actually receive.

10.3. Statistical Analyses

10.3.1. General Statistical Considerations

Statistical analysis of this study will be the responsibility of Lilly or its designee. Any change to the data analysis methods described in the protocol will require an amendment ONLY if it changes a principal feature of the protocol. Any other change to the data analysis methods described in the protocol, and the justification for making the change, will be described in the SAP or the clinical study report (CSR). Additional exploratory analyses of data will be conducted as deemed appropriate.

The primary analysis is for the treatment period through Week 26. The primary endpoint is the HbA1c measurement obtained at Week 26 (Visit 18).

Efficacy analyses will be conducted on all randomized patients using an intention-to-treat (ITT) approach according to the treatment the patients are assigned. Efficacy analyses, including the analyses for the primary and multiplicity adjusted objectives, will include data collected prior to permanent discontinuation of IP through Week 26. When change from baseline is included as a response variable of analysis models, the patient will be included in the analysis only if he/she has a baseline and a postbaseline measurement. Selected efficacy analyses will also be conducted using the Per-Protocol (PP) and Completer populations.

Safety analyses will be conducted on the Safety population. Analyses of AEs will include 2 sets of analyses, unless otherwise specified. The first set of analyses will include data collected prior to permanent discontinuation of IP. The second set of analyses will include all data collected during the course of the entire study regardless of IP use. Analyses of hypoglycemia will be conducted on data collected prior to permanent discontinuation of IP, while analyses for post-treatment may be conducted as needed. Analyses of safety laboratory measurements will be performed on all data collected during the planned treatment period regardless of IP use. Week 26 analyses will include treatment comparisons between the 2 treatment groups.

Unless otherwise noted, all tests of treatment effects will be conducted at a 2-sided alpha level of 0.05, and CIs will be calculated at 95%, 2-sided. All tests of interactions between treatment groups and other factors will be conducted at a 2-sided alpha level of 0.10.

A graphical approach for multiple comparisons (Bretz et al. 2011) will be used to strongly control the overall Type I error (2-sided alpha level of 0.05) for testing the treatment effect for the primary and multiplicity adjusted objectives.

Baseline is defined as the last nonmissing measurement at or before the randomization visit, (Visit 8) unless otherwise specified.

The primary analysis method will be a restricted maximum likelihood-based, mixed-effect model repeated measure (MMRM) analysis using all the longitudinal observations at each scheduled postbaseline visit. The model for the analysis of the primary efficacy endpoint of change from baseline in HbA1c will include the fixed class effects of treatment, strata (country, type of basal insulin, and metformin use at study entry), visit, and treatment-by-visit interaction, as well as the continuous, fixed covariate of baseline value. For analyses of variables other than HbA1c, the HbA1c stratum (\leq 8.5%, >8.5%) will be included in the model. An unstructured covariance structure will be used to model the within-patient errors. Significance tests will be based on least squares (LS) means and Type III tests. SAS PROC MIXED will be used to perform the analysis. If this analysis fails to converge, the following covariance structures will be tested in order:

- Toeplitz with heterogeneity
- Autoregressive with heterogeneity
- Compound symmetry with heterogeneous variances
- Toeplitz

- Autoregressive
- Compound symmetry without heterogeneous variances.

The first covariance structure that converges will be used. The Kenward-Roger approximation will be used to estimate denominator degrees of freedom.

An analysis of covariance (ANCOVA) model for the change from baseline to the Week 26 HbA1c endpoint with strata (country, type of basal insulin, and metformin use at study entry), and treatment as fixed effects and baseline as a covariate will be conducted as supportive analyses. Missing endpoints will be imputed using the last-observation-carried-forward (LOCF) approach, using only postbaseline data. For analyses of variables other than HbA1c, the HbA1c stratum ($\leq 8.5\%$, $\geq 8.5\%$) will be included in the model.

For continuous measures, summary statistics will include sample size, mean, SD, median, minimum, and maximum for both the actual and the change from baseline measurements. Least squares means and standard errors derived from the analysis models will also be displayed for the change from baseline measurements. Treatment comparisons will be displayed showing the treatment difference LS means and the 95% CIs for the treatment differences, along with the p-values for the treatment comparisons.

For categorical measures, summary statistics will include sample size, frequency, and percentages. Fisher's exact test will be used for treatment comparisons.

10.3.2. Treatment Group Comparability

10.3.2.1. Patient Disposition

A detailed description of patient disposition will be provided. Frequency counts and percentages of all patients entered, enrolled, randomized, completing, and/or discontinuing from the study will be presented for each treatment group. Reasons for discontinuation from study treatment and from the study during the treatment period will be summarized and compared between treatment groups using Fisher's exact test. Reasons for discontinuation from the study during the lead-in and follow-up periods will be summarized.

10.3.2.2. Patient Characteristics

Standard baseline characteristics of age, sex, ethnicity, race, height, weight, and BMI will be summarized for all randomized patients. Summary statistics will include sample size, mean, SD, median, minimum, and maximum for continuous measures and sample size, frequency, and percent for categorical measures. Comparisons between treatment groups will be performed using Fisher's exact test for categorical data and an analysis of variance (ANOVA) with treatment in the model for continuous data. Baseline diabetes characteristics will be summarized in a similar manner.

Medical history and AEs at baseline will be summarized by preferred term (PT) within system organ class (SOC), and comparison between treatment groups will be performed using Fisher's exact test.

10.3.2.3. Concomitant Therapy

The type of insulin therapy at study entry and at baseline will be compared between treatment groups using Fisher's exact tests. The dose of basal and bolus insulin therapy during the lead-in period will be compared between treatment groups using an ANOVA with treatment in the model.

Concomitant medications used during the treatment period will be summarized and compared between treatment groups using Fisher's exact test.

10.3.3. Efficacy Analyses

10.3.3.1. Primary Analyses

The primary objective of this study is to test the hypothesis that LY900014 is noninferior to insulin lispro on glycemic control (NIM=0.4% for HbA1c) in patients with T1D, when administered as prandial insulin (0-2 minutes prior to the meal), in combination with basal insulin for 26 weeks.

The primary efficacy comparison will be based on the contrast between LY900014 and insulin lispro at Week 26 (Visit 18) from the MMRM analysis of change from baseline in HbA1c using all randomized patients. If the upper limit of the 2-sided 95% CI for the LS mean difference in the change from baseline in HbA1c for LY900014 minus insulin lispro is below +0.4%, LY900014 will be declared noninferior to insulin lispro. The analysis model and selection of covariance structure is described in Section 10.3.1.

10.3.3.1.1. Additional Analyses for the Primary Endpoint

The primary analysis model, MMRM, will be repeated using the PP and Completer populations to check the sensitivity of the analysis. If the conclusion differs from that of all randomized patients, the data and analyses will be further investigated.

A secondary analysis model will be an ANCOVA for HbA1c change from baseline to Week 26 (Visit 18), using the model described in Section 10.3.1. Missing endpoints will be imputed using the LOCF approach using postbaseline data only.

In addition to the primary objective, the superiority of LY900014 in controlling HbA1c compared to insulin lispro will also be assessed with the same model using all randomized patients. If the p-value is less than the alpha level from the graphical approach allocated to this hypothesis, LY900014 will be declared superior to insulin lispro.

10.3.3.2. Secondary Analyses

A graphical approach for multiple comparisons will be used to strongly control the overall Type I error (2-sided alpha level of 0.05) for testing the treatment effect for the primary and the following multiplicity adjusted objectives: superiority of LY900014 compared with insulin lispro for 1-hour PPG excursion at Week 26, 2-hour PPG excursion at Week 26, and change from baseline to Week 26 in HbA1c.

An ANCOVA model with strata (country, type of basal insulin, metformin use at study entry, and baseline HbA1c strata [\leq 8.5%, >8.5%]) and treatment as fixed effects and baseline as a

covariate will be used to analyze the 1-hour and 2-hour PPG excursions. However, if the percentage of the patients with missing MMTT data at baseline is higher than 15%, a constrained longitudinal data analysis model (Liu et al. 2009; Lu 2010) will be used instead. Analyses details will be documented in the SAP.

Hemoglobin A1c and change from baseline in HbA1c at all time points will be analyzed by the same MMRM model used for the primary analysis.

Additional continuous secondary efficacy variables, as well as the change from baseline for these variables, will be analyzed either by the MMRM or ANCOVA models described in Section 10.3.1.

Treatment comparisons for the proportion of patients with HbA1c <7.0% and \leq 6.5% will be analyzed using a longitudinal logistic regression with repeated measurements conducted by a generalized linear mixed model including independent variables of treatment, baseline HbA1c value, visit, baseline HbA1c by visit interaction, and treatment by visit interaction. An unstructured covariance structure will be used. As a sensitivity analysis, the proportion of patients with HbA1c <7.0% and \leq 6.5% at Week 26 (Visit 18), imputed using LOCF, will be compared using a logistic regression model including treatment and baseline HbA1c value in the model.

Actual and change from baseline in basal, prandial, and total dose, as well as the prandial/total insulin dose ratio, will be analyzed by the MMRM models described in Section 10.3.1.

10.3.3.3. Tertiary/Exploratory Analyses

Continuous variables and the change from baseline for these variables will be analyzed either by the MMRM or ANCOVA models described in Section 10.3.1. Categorical variables will be analyzed either by model (for example, logistic regression) or by Fisher's exact test. Analysis details for the tertiary endpoints will be described in the SAP.

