To compare the incidence of treatment-emergent positive anti-insulin lispro antibodies for LY900014 and insulin lispro	Incidence of treatment-emergent positive anti- insulin lispro antibodies			
 To compare LY900014 and insulin lispro with respect to quality of life as measured by the EQ- 5D-5L 	 Change from baseline in EQ-5D-5L UK-population based health state index score and EQ-VAS score at Week 26 			
To compare LY900014 and insulin lispro with respect to diabetes treatment satisfaction as measured by the ITSQ	Change from baseline in ITSQ regimen inconvenience and lifestyle flexibility domain scores at Week 26			
To compare LY900014 and insulin lispro with respect to the impact that diabetes has on the ability to work and perform regular activities as measured by the WPAI-GH	Change from baseline in WPAI-GH item scores at Week 26			
To compare LY900014 and insulin lispro with respect to changes in body weight	Change in weight (kg) from baseline to Week 26			
To compare LY900014 and insulin lispro with respect to glycemic variability	Within-day and between-day glycemic variability measured by the standard deviation and the coefficient of variation of 10-point SMBG profiles			

Abbreviations: 1,5-AG = 1,5-Anhydroglucitol; EQ-5D-5L = European Quality of Life – 5 Dimensions 5 Level; EQ-VAS = EuroQol visual analog scale; HbA1c = hemoglobin A1c; ITSQ = Insulin Treatment Satisfaction Questionnaire; MMTT = mixed-meal tolerance test; NIM = non-inferiority margin; PPG = postprandial glucose; SMBG = self-monitored blood glucose; T1D = type 1 diabetes mellitus; WPAI-GH = Work Productivity and Activity Impairment General Health.

5. Study Design

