10.3.4. Safety Analyses

Safety measures will include AEs, hypoglycemia, vital signs and weight, treatment exposure, laboratory measures, and antibodies to insulin lispro. Analyses will be performed on data collected from randomization through Week 26 for all 2 treatment groups.

Events that are newly reported after the first dose of IP or reported to worsen in severity from baseline will be considered treatment-emergent adverse events (TEAEs). The Medical Dictionary for Regulatory Activities (MedDRA) lowest level term (LLT) will be used in the treatment-emergent assessment. The maximum severity for each LLT during the baseline period will be used as baseline severity.

Serious adverse events, AEs reported as reason for discontinuation from the IP or study, and TEAEs will be summarized in tables using the MedDRA PT, sorted by decreasing frequency within the LY900014 treatment group. Treatment-emergent adverse events will also be summarized by PT sorted by decreasing frequency within SOC for all TEAEs and TEAEs by maximum severity. For events that are specific to only 1 sex, the denominator and computation

of the percentage will include only patients from the given sex. The number and proportion of patients with at least 1 event for each type of event will be summarized and compared between treatment groups using Fisher's exact test. Serious adverse events, AEs reported as reason for discontinuation from the IP or study, and TEAEs will also be summarized for open-label insulin lispro during the lead-in period. Symptoms solicited by questionnaires will not be considered spontaneous AEs for analysis.

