#### 6.12.6. Vital Signs and Other Physical Findings

Postbaseline measurements and change from baseline to postbaseline for vital signs and physical characteristics (systolic blood pressure [SBP], diastolic blood pressure [DBP], pulse rate, weight, BMI) at the scheduled visits will be summarized for patients who have both baseline and at least 1 postbaseline result.

The measurements during the treatment period (0 to 26) will be analyzed by an MMRM model with treatment, baseline value of the response variable, visit, and visit by treatment interaction as fixed factors and patient as the random factor.

Weight during the lead-in period will also be analyzed by an MMRM model with Visit 2 value of the response variable, randomized treatment, visit, and treatment-by-visit interaction as fixed factors and patient as the random factor in all randomized patients.

An ANCOVA model will also be used for the analysis of the last nonmissing observation (including early discontinuation) during the treatment period and during the entire study (up to Visit 801). The ANCOVA models are the same as those used for clinical laboratory measures.

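### The protocol places body weight under two sets of analysis rules; SAP 6.12.6 takes the safety route without saying so and leaves all four randomization factors out of the weight model

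*Protocol*

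**What the plan says.** Protocol Table ITSD.1 lists among the tertiary/exploratory objectives "To compare LY900014 and insulin lispro with respect to changes in body weight", with the endpoint "Change in weight (kg) from baseline to Week 26". This is a separate row from the general safety objective, which covers adverse events, vital signs, chemistry and hematology.

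Protocol 10.3.3.3 covers tertiary outcomes: "Continuous variables and the change from baseline for these variables will be analyzed either by the MMRM or ANCOVA models described in Section 10.3.1". It then adds "Analysis details for the tertiary endpoints will be described in the SAP". The Section 10.3.1 MMRM contains "strata (country, type of basal insulin, and metformin use at study entry), visit, and treatment-by-visit interaction", along with treatment and baseline, and the Section 10.3.1 ANCOVA carries the same three strata. A further rule brings in the fourth randomization factor: "For analyses of variables other than HbA1c, the HbA1c stratum" goes into the model as well.

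Protocol 10.3.4 also claims weight: "Safety measures will include AEs, hypoglycemia, vital signs and weight, treatment exposure, laboratory measures, and antibodies to insulin lispro". It assigns continuous safety variables to MMRM or ANCOVA, without listing terms and without pointing back to Section 10.3.1.

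SAP 6.12.6 models weight together with the vital signs during treatment, "with treatment, baseline value of the response variable, visit, and visit by treatment interaction as fixed factors". Its last-observation ANCOVA is the laboratory one from SAP 6.12.5, with treatment and baseline only. Country, basal insulin type, metformin use and HbA1c stratum appear in neither.

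**The concern.** Weight is a between-arm objective in its own right, and the only protocol section that gives terms for tertiary continuous outcomes includes the strata. The SAP keeps all four factors for other tertiary outcomes: the ITSQ scores (SAP 6.11.6), the WPAI-GH scores (SAP 6.11.7, by reference to the ITSQ model) and SMBG glycemic variability (through the SAP 6.11.5 MMRM). Weight is treated differently. Neither SAP 6.12.6 nor the SAP revision history gives a reason or says which protocol section is being followed.

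Two things are at stake, both small. First, a model that ignores factors used to stratify randomization overstates the standard error when those factors predict the outcome, so the test becomes somewhat conservative. For a comparison of weight gain, that makes it slightly harder to show a difference between arms. Second, an unsettled reading of the protocol leaves room for argument about the right model after the results are known.

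**Working it through.** **1. The text, side by side.**

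| Source | Weight classed as | Model terms besides treatment, baseline and visit terms |
|---|---|---|
| Protocol Table ITSD.1, 10.3.3.3 and 10.3.1 | tertiary objective | country, basal insulin type, metformin use, HbA1c stratum |
| Protocol 10.3.4 | safety measure | not given |
| SAP Table 4.1, objective 17 | tertiary objective | – |
| SAP 6.12 and 6.12.6 | safety measure | none |

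The SAP agrees with the second row and not with the first. SAP 6.2 uses the stratification factors for efficacy endpoints and includes them in other analyses only where Sections 6.11 and 6.12 say so. For weight, 6.12 does not.

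**2. The plan's own figures.** No design figure is given for weight. The only one stated is for HbA1c (Protocol 10.1): margin 0.4%, SD 1.1%, 149 per arm, 87% power.
- 0.4 / (1.1 × √(2/149)) = 3.14, and 3.14 − 1.96 = 1.18, which gives 88.1% power (87.9% with the t distribution).
- 298 / 0.85 = 350.6, against about 350 stated.

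Both agree with the plan within rounding, and neither depends on the weight model.

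**3. Interval width.** Let R² be the share of weight variance left after baseline that the four binary factors explain. With N = 298, the model without strata has 298 − 3 = 295 degrees of freedom and the model with strata has 298 − 7 = 291. The ratio of widths, without to with, is

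t(295) / [t(291) × √(1 − R²)].

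| Assumed R² | Extra width without strata |
|---|---|
| 0 | 0% |
| 0.01 | 0.5% |
| 0.02 | 1.0% |
| 0.05 | 2.6% |
| 0.10 | 5.4% |
| 0.20 | 11.8% |

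With N = 350 the figures are the same to this precision.

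**4. What R² might be.** The documents give neither an SD for weight change nor any stratum effect, so these inputs are assumptions, apart from the 20% country share, which is 70/350 planned patients.
- Stratum shares: 35% (HbA1c), 20% (country), 20% (basal type), 8% (metformin).
- Stratum differences: 0.3–1.0, 0.3–0.8, 0.2–0.4 and 0.5–1.0 kg, in the same order.
- SD of weight change: 2.5–3.5 kg.

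Treating the factors as independent, R² = Σ p(1 − p)d² / SD².
- Low end: (0.0205 + 0.0144 + 0.0064 + 0.0184) / 12.25 = 0.0597 / 12.25 = 0.0049.
- High end: (0.2275 + 0.1024 + 0.0256 + 0.0736) / 6.25 = 0.4291 / 6.25 = 0.0687.

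Adding the strata would then narrow the interval by 1 − √(1 − R²), or 0.24% to 3.5%. In kilograms, the half-width 1.96 × SD × √(2/149) is 0.57 kg at SD 2.5 and 0.79 kg at SD 3.5. The change is about 0.57 × 0.035 = 0.02 kg at the high end and 0.79 × 0.0024 = 0.002 kg at the low end.

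**5. Simulation.** ANCOVA with stratified blocks of 4, N = 298, 3,000 runs per value of R², with block size and factor prevalences assumed.

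| R² | Type I error, no strata | Type I error, strata | SD of estimate, no strata / strata |
|---|---|---|---|
| 0 | 0.050 | 0.050 | 0.115 / 0.115 |
| 0.02 | 0.046 | 0.048 | 0.113 / 0.114 |
| 0.05 | 0.036 | 0.040 | 0.109 / 0.109 |
| 0.10 | 0.037 | 0.045 | 0.109 / 0.109 |
| 0.20 | 0.032 | 0.049 | 0.105 / 0.104 |

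The Monte Carlo error of each rate is about √(0.05 × 0.95 / 3000) = 0.004, so only the general direction should be read from these columns. Bias was about zero throughout. The estimate is nearly as precise either way, because stratified randomization already supplies the balance. What changes is the reported standard error, which is too large when the strata are left out. These checks use a single-visit ANCOVA; the MMRM was not simulated.

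**The case against.** The strongest reply is that the SAP does not depart from the protocol at all. Section 10.3.3.3 sits under efficacy analyses. Section 10.3.4 names weight next to vital signs and, unlike the text for secondary, tertiary and health-outcome variables, does not refer to Section 10.3.1. The tertiary list also contains vital signs and laboratory measures. If being listed there were enough to require strata, all of those models would be departures too, which nobody would claim. SAP 6.2 states a rule for strata, and the liver, laboratory and antibody models follow it in the same way. Protocol 10.3.3.3 leaves tertiary detail to the SAP.

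Most of this stands. A reader might infer that the SAP contradicts the protocol; the documents do not support that, because Section 10.3.4 offers a reading under which SAP 6.12.6 conforms. A reader might also infer that the lack of a stated reason breaks the rule that changes of method be justified. That does not follow either: Protocol 10.3.1 lets the justification appear in the SAP or the clinical study report, and the report is not available here.

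The argument that the strata must predict weight is also open to question. Metformin is stopped at Visit 2, about eight weeks before randomization, and SAP Table 6.2 takes baseline weight as the last of Visits 2–8. Part of any effect of stopping it therefore falls before baseline.

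What remains is that weight, unlike the vital signs and laboratory tests, has its own comparative objective outside the general safety row. Section 10.3.4 neither gives terms nor asks for the strata to be left out, and the SAP does not say which route it chose.

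**Conclusion.** The point holds as an ambiguity that the SAP resolved without saying so, together with a small and free improvement to one model. The weight analysis as planned is valid: the estimate is unbiased and the test errs on the conservative side. The interval is about 0 to 3% wider than with the strata if R² lies between 0 and 0.05. The assumed effects in the working reach an R² of 0.07, which would add about 1/√(1 − 0.0687) − 1 = 3.6%. R² is unknown from the documents and could be zero, so a loss of precision is possible but not shown. It would be wrong to read this as a biased analysis or as a demonstrated loss of power. Weight is tertiary and outside the multiplicity scheme, and no primary or multiplicity-adjusted conclusion changes.

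**What to change.** In SAP 6.12.6, add country (China vs Other), type of basal insulin, metformin use at study entry and HbA1c stratum as fixed effects to the treatment-period weight MMRM and to the weight ANCOVA, as in SAP 6.11.5 and 6.11.6. Add one sentence stating that weight follows Protocol 10.3.3.3. That sentence should be limited to the model terms, so that the analysis population and baseline set for weight in SAP Table 6.2 are left as they are.

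The factors are already collected in the database (SAP 6.2). The cost is the wording, about four degrees of freedom, and a weight model that no longer matches the vital-sign models in the same section. If the sponsor prefers the present model, a sentence saying that weight follows Protocol 10.3.4, and why, would remove the ambiguity but leave the interval conservative to whatever extent the strata matter. Either change should be made before unblinding.
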